**Outcome measures related to estimated inhibitory concentrations:**

25. The concentration of TB31F in serum that provides >80% reduction in the average proportion of infected mosquitoes as measured in DSF after TB31F administration
26. The concentration of TB31F in serum that provides >80% reduction in the average proportion of infected mosquitoes as measured in DMFA after TB31F administration
27. The concentration of TB31F in serum that provides >80% transmission blocking activity relative to experimental controls as measured in SMFA after TB31F administration
28. The concentration of TB31F in serum that provides >80% reduction in the average mosquito infection intensity (oocyst number) as measured in DSF after TB31F administration
29. The concentration of TB31F in serum that provides >80% reduction in the average mosquito infection intensity (oocyst number) as measured in DMFA after TB31F administration
30. The concentration of TB31F in serum that provides >80% transmission reducing activity relative to experimental controls as measured in SMFA after TB31F administration

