### Efficacy outcome measures

#### **Efficacy outcome measures related to within-group % reduction in proportion infected mosquitoes:**

We will determine averaged within-individual percent reduction in the proportion of mosquitoes infected at days post-treatment (1, 5, 14) compared to baseline (day 0) for each group. This will be assessed through DMFA and DSF and outcomes for these different feeding assays will be presented separately as percentage reduction (with 100% as total reduction of transmission, and negative values as enhanced transmission) with 95% confidence interval. Data will be analysed for all individuals who received the product per protocol and only for those individuals who are infectious at baseline (i.e. infecting at least one mosquito with any number of oocysts). All analyses on within-individual percentage reduction in the proportion of infected mosquitoes will use a mixed effects generalized linear model assuming a binomial error structure and a log-link, using individual mosquito data with day of follow-up and dose of TB31F and their interaction as fixed effects. A random intercept will be added to models to allow for participant-level variation in pre-intervention transmissibility and thus account for the correlation between outcomes for mosquito samples from the same participant (i.e. intra-cluster correlation).

In exploratory analyses, these analyses will be performed following stratification for naturally acquired transmission reducing immunity, as quantified by SMFA at baseline (pre-TB31F administration) samples.

The impact of naturally acquired transmission reducing immunity, assessed in baseline samples by SMFA (TRA>50%; TRA>80%) and by antibody prevalence to known gamete antigens Pfs230 and Pfs48/45, on infecting mosquitoes will also be determined. For this, TRA as categorical variable and antibody prevalence (binary variable), will be added as fixed effects to mixed effects logistic regression models on proportion infected mosquitoes at baseline (pre-TB31F administration). These models may be expanded to include human genetic factors (e.g. a fixed effect for HbAS or HbAC carriage as compared to wild-type HbAA).

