### Outcome measures related to estimated inhibitory concentrations:

Transmission blocking activity (TBA, the reduction in the proportion of infected mosquitoes) and transmission reducing activity (TRA, the reduction in oocyst numbers/infection intensity) will be determined for DMFA and DSF separately. Baseline infection prevalence and intensity estimates will be used to calculate relative reductions in these transmission measures during follow-up. For SMFA experiments, TRA will be quantified as the relative reduction in oocyst intensity for test samples (one feeder per test sample) compared to pooled naïve serum controls (two feeders). Samples may be tested in one or two independent SMFA experiments.

TRA values for each participant and time-point will be estimated using mixed effect negative binomial regression models with random intercepts for each experiment to account for between experiments differences in oocyst intensity that is achieved in control experiments (SMFA) or baseline measurements (DMFA/DSF).

TBA values for each participant and time-point will be estimated using mixed effect logistic regression models with random intercepts for each experiment to account for between experiments differences in oocyst prevalence that is achieved in control experiments (SMFA) or baseline measurements (DMFA/DSF). Of note: for SMFA TBA estimates are deemed to be less informative than TRA estimates due to the design of these experiments that aim for high oocyst prevalence and density in control experiments.

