TRA and TBA estimates will be correlated with TB31F antibody measures to obtain the best possible fit for DMFA, DSF and SMFA separately. This will allow us to estimate IC50 and IC80 values for TB31F for each assay separately and model TRA and TBA estimates based on antibody concentration. TRA/TBA modeling is relevant because the precision of these estimates decreases with decreasing activity. Samples with lower levels of TRA (typically below 80%) and TBA may thus have relatively imprecise estimates. For some analyses, we may thus use TRA or TBA estimates that are inferred from antibody concentration based on the best fit model for the association between antibody concentration and TRA or TBA. For this fit, will use mixed effects models, similar to methods described by Miura et al. and Ramjith et al, adjusting TB31F antibody concentrations measured in serum to reflect whole blood concentrations. These models will estimate Inhibitory Concentration values (e.g. IC80, IC50) based on the best fit.

TB31F concentration in serum at which 80% TRA is expected (IC80) is calculated through (mixed-effects) linear regression by regressing the square root of serum concentration on the log-mean

oocyst ratio, i.e.  $IC_{80} = \left( \frac{\left( \log\left(\frac{100}{100-80}\right) - \hat{\beta}_0 \right)}{\hat{\beta}_1} \right)^2$  where  $\hat{\beta}_0$  and  $\hat{\beta}_1$  are the estimated regression coefficients

for the intercept and slope of the linear model respectively. The delta method will be used to estimate the standard error for the IC80 value and thus a 95% confidence intervals for the IC80 can be calculated. To compare assays (SMFA/DMFA/DSF) we can include a categorical variable in the model as an interaction variable to allow different slopes ( $\hat{\beta}_1$ ) to be estimated for the different assays.

Thereafter comparisons can be drawn for the IC80 values between assays. A similar calculation is made for IC50 values.

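### The IC80/IC50 formula squares a root without requiring it to be non-negative, so a threshold already exceeded at zero fitted concentration, or a falling fitted slope, is reported as an ordinary positive concentration

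*SAP*

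**What the plan says.** All references are to the SAP. Under Analysis Methods, the section on estimated inhibitory concentrations defines the IC80 as the "TB31F concentration in serum at which 80% TRA is expected" and gives IC80 = ((log(100/(100−80)) − b0)/b1)², where b0 and b1 "are the estimated regression coefficients" for intercept and slope. It adds that "A similar calculation is made for IC50 values". On precision it says "The delta method will be used to estimate the standard error" of the IC80, from which a 95% confidence interval follows. IC80 values may then be compared between SMFA, DMFA and DSF.

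The same section fixes the references. SMFA activity is measured "compared to pooled naïve serum controls (two feeders"), and DMFA and DSF activity against baseline feeds. Outcomes 25 to 30 are all defined at the 80% level, for example outcome 30: "The concentration of TB31F in serum that provides >80% transmission reducing activity relative to experimental controls as measured in SMFA after TB31F administration". The IC50 is not a listed outcome; it appears only in the analysis section.

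Nowhere does the SAP restrict the sign of b1 or of the root. Nor does it say what is reported if the threshold is never reached, is already exceeded at zero concentration, or lies beyond the concentrations tested.

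**The concern.** A square is never negative. If the fitted line meets the threshold only at a negative value of the square root of concentration, no concentration solves the equation, yet the formula still prints a positive one. Nothing in the printed value shows that it is invalid.

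This can come about in three ways:

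- **Background activity in SMFA.** The reference is naïve serum, so natural activity in the fitted samples enters the intercept. The intercept exceeds the threshold if average fitted background TRA is above 50% (IC50) or 80% (IC80).
- **Only treated feeds near saturation are fitted.** The response is then nearly flat over the observed range, and extrapolating the line back to zero inflates the intercept. This needs no natural immunity and can affect any assay.
- **A negative fitted slope.** This is less plausible.

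At stake are the exploratory potency estimates and their comparison between assays. SMFA uses naïve serum and DMFA/DSF use baseline, so a folded SMFA value could be read as a true difference in potency between assays.

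**Working it through.** The SAP prints a formula but no IC value, so there is no figure of its own to reproduce. The formula is checked instead.

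**Inputs.** Thresholds from the SAP formula: L80 = log(100/20) = 1.609 and L50 = log(100/50) = 0.693. The slope b1 is not in the SAP; 0.8 and 0.6 are assumed. Background TRA enters as b0 = −log(1 − background).

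**1. The formula is the right inverse inside its domain.** The model is log ratio = b0 + b1√C. Setting this equal to L gives √C = r = (L − b0)/b1, hence C = r² if r ≥ 0. With b0 = 0.1 and b1 = 0.6, r = 1.509/0.6 = 2.516 and C = 6.33. Fitted TRA at that concentration is 80.0%, as intended. (The SAP's words, "regressing the square root of serum concentration on the log-mean" oocyst ratio, describe the reverse regression. That is a separate matter, not pursued here.)

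**2. Sign of the slope.** With b0 = 0:
- b1 = +0.8: r = 2.012, IC80 = 4.05.
- b1 = −0.8: r = −2.012, IC80 = 4.05.

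In the second case the fitted log ratio at C = 4.05 is −0.8 × 2.012 = −1.609. Fitted TRA is then 1 − e^1.609 = −400%, a five-fold enhancement.

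**3. Intercept above the threshold.** With b1 = 0.8:

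| Fitted background TRA | b0 | r for IC50 | Printed IC50 (µg/mL) |
|---|---|---|---|
| 0% | 0 | 0.866 | 0.75 |
| 25% | 0.288 | 0.507 | 0.26 |
| 50% | 0.693 | 0 | 0.00 |
| 75% | 1.386 | −0.866 | 0.75 |
| 80% | 1.609 | −1.145 | 1.31 |
| 90% | 2.303 | −2.012 | 4.05 |

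At 75% background the printed IC50 equals that for no background. Fitted TRA at that concentration is 1 − exp(−(1.386 + 0.693)) = 87.5%, not 50%. The IC80 turns in the same way at 80% background: with b1 = 0.6 it is 0 at 80%, 0.23 at 85% and 1.33 at 90%. The turning points do not depend on the slope.

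**4. Whether the interval reveals it.** The derivatives of r² are −2r/b1 with respect to b0 and −2r²/b1 with respect to b1. Both vanish at r = 0, so the delta-method standard error is exactly zero at the fold. Beyond it the interval looks ordinary. With b1 = 0.6, assumed standard errors of 0.1 (b0) and 0.05 (b1) and correlation −0.6, a 75% background gives IC50 1.33 with standard error 0.55. The interval 1.33 ± 1.96 × 0.55 runs from about 0.25 to 2.41.

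**5. No effect.** If the error in b1 dominates, SE(IC)/IC ≈ 2·SE(b1)/|b1|. The 95% interval then excludes zero only if |b1|/SE(b1) > 2 × 1.96 = 3.92, which is rare when the true slope is zero. Simulation agrees. Settings (all assumed): 40, 90 or 180 samples, a third at zero concentration, the rest log-normal with median 5 µg/mL and log SD 0.8, log-ratio SD 1, background log ratio 0 or 0.7. The interval excluded zero in under 1% of fits for both IC80 and IC50. At n = 40 the point estimate of the IC50 fell inside the tested range in 23% of fits (background 0) or 80% (background 0.7), so the interval, not the estimate, gives the warning.

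**6. True effect, by samples fitted.** Simulated DMFA-type data with treated feeds only, under varied assumed potencies (IC80 1 to 4 µg/mL), concentrations and oocyst counts, gave negative IC50 roots in 0 to 100% of fits and negative IC80 roots in 0 to 91%. With zero-concentration saline participants in the fit, the figures were at most 3% and 0%.

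**The case against.** Much can be said for the plan, and most of it stands.

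- **No effect.** A reader might infer that the rule yields a potency value whether or not the antibody works. The SAP does not support that once the planned interval is read with the estimate: under no effect it almost always includes zero. At a slope of exactly zero the formula is undefined; at ±0.01 (b0 = 0) it gives an IC80 of about 25,900, which nobody would take at face value.
- **Natural immunity.** A reader might infer that the SAP expects background above 50% or 80%. The cut-offs in its efficacy sections classify individuals. The SAP says only that participants may have natural activity and gives no prevalence. The error needs the fitted average above the threshold, and in DMFA and DSF the baseline reference largely cancels background.
- **Enhancement.** The phrase "negative values as enhanced transmission" is a reporting convention for percent reductions, not a forecast. The sample size section plans for a 90% reduction. The planned plot of modelled against observed activity would probably also expose a falling slope.
- **Samples fitted.** Baseline and control samples are planned for SMFA. If they enter the fit, negative roots almost disappear.
- **Importance.** The IC objectives are exploratory, and the IC50 is not a listed outcome.

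Two things remain. The interval gives no protection when the intercept is well above the threshold or enhancement is strong. And the inhibitory-concentration section does not say which samples enter the fit, so the protective case is likely but not guaranteed.

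**Conclusion.** The point holds as a minor defect in a fixed formula. Outside b1 > 0 and r ≥ 0 the printed expression returns a wrong concentration and, when the intercept is above the threshold, one that worsens as activity increases. The sign symmetry and the turning points at 50% and 80% are exact. The µg/mL values rest on assumed slopes. The simulated frequencies depend so strongly on assumptions that they are not forecasts: from 0 to 100% for treated-only fits, and near zero when zero-concentration samples are included.

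It would go too far to conclude that the potency analysis cannot tell an active antibody from an inactive one, or that the trial's efficacy conclusion is at risk. The primary DMFA analysis does not use this formula. What is exposed is the exploratory IC80 and IC50 and their comparison between assays.

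**What to change.** In the analysis section on inhibitory concentrations, state that r = (threshold − b0)/b1 is computed first and squared only if b1 > 0 and r ≥ 0. Otherwise report as follows:

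- b1 ≤ 0: *not estimable: no increasing concentration-response*.
- b1 > 0 and b0 above the threshold: *threshold already exceeded at zero fitted TB31F concentration; IC not estimable*. This wording avoids presenting background activity as high TB31F potency.
- r² above the highest concentration tested: *> highest concentration tested*.

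Apply the rule to IC80 and IC50 in each assay before assays are compared. A stricter condition, such as a lower confidence limit for b1 above zero, is optional; the algebra does not need it.

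The cost is a few sentences and one check in the code. The downside is that some assays may have no point estimate.

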## Sample size

The sample size is standard for the safety cohorts without formal sample size estimation. Sample size is informed by the anticipated efficacy from an earlier Phase I study and the transmission blocking effects observed in similar Malian cohorts when treated with transmission blocking drugs; this is done for the efficacy cohort only. This sample size for the efficacy cohort (n=30 per group) will give us 97% empirical power to detect >80% reduction in infectivity (defined as the percentage of mosquitoes with at least one oocyst) with a one-tailed test with a 0.025 level of significance when dissecting at least 40 mosquitos per participant at each timepoint. This power calculation is based on an online tool based on mixed effects logistic regression, an expected reduction in infectivity of 90%, an expected baseline proportion of infectivity of 15% for the average participant (accounting for non-infectious participants), and a conservative expected intra-cluster correlation of 0.5. Of note, this includes non-infectious individuals. In the four years that we performed NECTAR studies with a highly similar

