study population, 66.0-79.5% of individuals infected at least one mosquito at enrolment with 14.2-17.0% of mosquitoes becoming infected. The power calculation given above includes all individuals (infectious and non-infectious). If we retain 30 individuals per arm and exclude those individuals who are not infectious at baseline ( $\leq 10$ ), the expected percentage of infected mosquitoes will increase from 15% (in the situation where some individuals infect no mosquitoes) to  $\sim 20\%$ . Based on a mixed effects logistic regression we looked at 200 simulations with an expected reduction in infectivity of 90%, an expected baseline proportion of infectivity of 20% for the average participant, and an expected intra-cluster correlation of 0.4. We estimated 91.5% empirical power to detect  $>80\%$  reduction in infectivity with a one-tailed test with a 0.025 level of significance when including 30 participants (of whom 20 are included in the analysis, i.e. after excluding non-infectious individuals) and dissecting 40 mosquitoes per participant at each timepoint. Importantly, these analyses are based on DMFA where venous blood is offered to mosquitoes. We and others have previously demonstrated that mosquito infection rates are at least 2-fold higher when allowing mosquitoes to feed directly on the skin of participants. When the expected baseline proportion infected mosquitoes is updated to account for higher infection rates by skin feeding (30% for the average participant) and we conservatively increase intra-cluster correlation to 0.8, we estimated 96% empirical power to detect  $>80\%$  reduction in infectivity with a one-tailed test with a 0.025 level of significance when including 30 participants and dissecting 40 mosquitoes per participant.

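### The IC80 sentence states the reverse of the regression its formula needs, and no rule covers the zero-oocyst feeds that will be common in DMFA and DSF

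*SAP*

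**What the plan says.** All of this is in the SAP section on outcome measures related to estimated inhibitory concentrations, unless stated otherwise.

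- The target is the "TB31F concentration in serum at which 80% TRA is expected". It is to be found by (mixed-effects) linear regression, "regressing the square root of serum concentration on the log-mean" oocyst ratio.
- The formula that follows is IC80 = ((log(100/(100−80)) − b0)/b1)². Its b0 and b1 "are the estimated regression coefficients" "for the intercept and slope of the linear model respectively". A delta-method interval, a comparison between assays through an interaction term, and a similar IC50 calculation follow.
- On the inputs to the fit: "TRA values for each participant and time-point will be estimated using mixed effect negative binomial regression models with random intercepts for each experiment". For DMFA and DSF the reference is the baseline feed: "Baseline infection prevalence and intensity estimates will be used to calculate relative reductions in these transmission measures during follow-up".
- The section gives no rule for a feed, or a baseline, without oocysts.
- The Sample size section reports that in similar earlier studies "66.0-79.5% of individuals infected at least one mosquito at enrolment with 14.2-17.0% of mosquitoes becoming infected". It plans on "an expected reduction in infectivity of 90"%, a 15% baseline in DMFA (30% in DSF) and 40 mosquitoes per participant and timepoint.

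**The concern.** There are two separate faults.

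**Direction.** To regress A on B makes A the outcome. The sentence therefore makes root concentration the outcome, while the formula treats it as the predictor. Only one linear model is described, and its intercept and slope are said to enter the formula. An analyst who codes the sentence and then applies the formula gets a wrong IC80, a wrong IC50, and intervals around the wrong values.

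**Zeros.** The log-mean ratio compares reference oocysts with test oocysts. It is infinite if the test feed has none and undefined or minus infinity if the baseline has none. All-zero test feeds come mainly from the samples with the strongest activity. Dropping them, or adding a constant, is a choice made after seeing data. Because zeros are expected in DMFA and DSF but hardly in SMFA, that choice could also look like a difference between assays.

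The results at stake are the oocyst-based inhibitory concentrations (outcomes 28–30). The SAP also allows TRA or TBA values inferred from concentration to be used in some analyses.

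**Working it through.** The SAP states no numerical IC80, so the check is of the formula and of how often zeros would arise.

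**1. Algebra of the formula.** Write y for the log-mean oocyst ratio and C for concentration. An 80% TRA corresponds to y = log(100/20) = log 5 = 1.609.
- Model needed: y = b0 + b1·√C. Setting y = log 5 gives C = ((log 5 − b0)/b1)², exactly the printed formula.
- Model as worded: √C = g0 + g1·y. Setting y = log 5 gives C = (g0 + g1·log 5)², a different expression.

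**2. Size of the direction error.** Assume b0 = 0, b1 = 0.9 and no noise.
- True IC80 = (1.609/0.9)² = 3.20.
- The worded regression gives g0 = 0 and g1 = 1/0.9. In the printed formula: (1.609 × 0.9)² = 2.10.
- For IC50, with log 2 = 0.693: true (0.693/0.9)² = 0.59; mismatched (0.693 × 0.9)² = 0.39.

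Noise adds to this, and the sign depends on the slope. In simulations with C uniform on 0.2–20:

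| Assumed slope | R² | True IC80 | Needed regression + formula | Worded regression + formula |
|---|---|---|---|---|
| 0.8 | 1 | 4.05 | 4.05 | 1.66 |
| 0.8 | 0.88 | 4.05 | 4.05 | 1.29 |
| 0.8 | 0.65 | 4.05 | 4.06 | 0.47 |
| 1.5 | 0.91 | 1.15 | 1.17 | 4.77 |

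**3. How often a feed has no oocysts.** A feed without oocysts is one with no infected mosquito. With post-treatment infection probability p and 40 mosquitoes, and ignoring variation between participants, P(zero) = (1 − p)⁴⁰.
- DMFA, 15% baseline, 90% reduction: p = 0.015, so 0.985⁴⁰ = 0.546.
- DMFA, 20% baseline (infectious participants only): 0.98⁴⁰ = 0.446.
- DSF, 30% baseline: 0.97⁴⁰ = 0.296.

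Now allow for variation between participants in the 15% case, with a logistic random intercept at the SAP's intra-cluster correlation of 0.5 (variance π²/3, SD 1.81). The answer depends on whether 15% is the mean over participants or the rate of the median participant, and on whether the 90% acts as a risk ratio or through an odds ratio.

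| Reading of 15% | Mosquitoes infected at baseline | Zero baselines | Zero after TB31F, all | Zero after TB31F, infectious at baseline |
|---|---|---|---|---|
| Mean | 15% | 23% | 66% (risk ratio); 75% (odds ratio matching a 90% mean reduction) | 58%; 68% |
| Median participant | 24% | 12% | 52% (risk ratio); 50% (odds ratio for the median participant) | 46%; 44% |

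The mean reading agrees with the SAP's enrolment data (14.2–17.0% of mosquitoes infected; zero baselines 100 − 79.5 = 20.5% to 100 − 66.0 = 34.0%). The median reading does not. Either way zeros are common.

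**4. Does the handling of zeros matter?** Two illustrative simulations, with assumed oocyst means, dispersion and slopes:
- True IC80 3.2, 14% zero feeds: dropping zeros 3.55 (+11%), adding 0.5 gives 3.85 (+20%), a count model 3.23 (+1%).
- True IC80 4.05, control mean 1 oocyst, 10% zero feeds: dropping zeros 3.33 (−18%); adding constants of 0.001 to 0.025 gives 3.35 to 4.03 (−17% to −0.5%).
- The second setting with an SMFA-like control mean of 20 oocysts: no zero feeds, and every option gives 4.00–4.03.

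**The case against.** The best defence on direction is that the formula follows directly from the sentence and is the exact inverse of the right model. An analyst who trusts the formula gets a valid IC80. This stands. A reader might infer that the IC80 will certainly be wrong, and the SAP does not support that: the error needs the worded regression to be fitted and its coefficients put into the formula.

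On zeros, the SAP does not speak of raw ratios. It estimates TRA with mixed negative binomial models, and it points to published methods that may deal with zeros and are not available here. Part of this stands: if participant-by-timepoint effects were shrunken random effects, an all-zero feed would not diverge. But the only random intercepts named at that step are per experiment. A separate TRA estimate for an all-zero feed would diverge, and the SAP itself gives no rule.

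A reader might also infer that zero handling biases the IC80 in a known direction. It does not: the two simulations moved opposite ways under different assumed oocyst densities.

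Finally, a reader might infer that this regression drives the duration-of-activity and dosing-regimen exploration. The SAP assigns that work to a non-linear mixed-effects PK/PD model and does not name the linear-regression IC80 as an input. The IC80 is an exploratory objective, and no primary or secondary efficacy objective rests on it.

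**Conclusion.** The concern holds in a limited form. The wording and the formula contradict each other; that is algebra and rests on no assumption. The example sizes (2.10 against 3.20 for IC80, 0.39 against 0.59 for IC50) rest on an assumed slope of 0.9 and arise only if the text is followed literally.

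The zero problem is real for DMFA and DSF. On the SAP's planning values, roughly half to two thirds of TB31F recipients would have an all-zero DMFA feed after treatment, and 20.5–34.0% of participants a zero baseline. The DMFA and DSF IC80, and the comparison with SMFA, would depend on an unstated choice. The shift of roughly 10–20% in either direction comes from assumed settings with only 10–14% zero feeds, so it illustrates sensitivity and does not predict the bias in this trial. SMFA is little affected because its controls are designed for high oocyst density.

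Since the analysis is exploratory and the remedy cheap, this should be corrected before the IC80 analysis is run, but it does not threaten the main efficacy results.

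**What to change.** 1. Reword the sentence so that the log-mean oocyst ratio is regressed on the square root of serum concentration. The formula and the delta-method step can stay; the same correction covers the IC50.
2. For DMFA and DSF, estimate IC80 and IC50 in one step from a mixed negative binomial model fitted to oocyst counts, with root concentration as covariate, control or baseline feeds as reference, and random intercepts for the participant or experiment. The concentration at which the modelled mean falls to 20% (or 50%) of the reference is the IC80 (or IC50). Zero feeds and zero baselines then enter as ordinary counts.
3. If the two-step fit is kept, state in advance how zero feeds and zero baselines enter it, and report the IC80 under at least one alternative rule, above all where assays are compared.

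The cost is one corrected sentence and a modest re-specification of an exploratory analysis. The model family is already in the SAP, and no additional data are needed.
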